## **Ethics and dissemination**

### *Informed consent*

Potential participants will be contacted personally prior to the operation by the anaesthesiologist or surgeon, who is in charge of the operation. The patients will receive oral and written information regarding:

- The trial, and that we would like to ask he/she to participate in the trial.
- That it is voluntary to participate, and the subject has the right to and is encouraged to take time to consider carefully if he/she wants to participate.

- The subject has the right to bring a friend or family member to the oral participant information
- That the trial is approved by “Datatilsynet” and “den Videnskabetiske Komité”
- That the subject at any time can cease to participate in the trial and if they do it will not have any consequences for further treatment
- Patient at Holstebro Hospital: We have established a biobank at Department of Clinical Biochemistry (Holstebro Hospital) and Department of Surgery (Zealand University Hospital). Their plasma for assessment of coagulation markers and NT-pro-BNP will be stored until further analysis.

The meeting will take place in a calm and quiet environment. Since all included patients require emergent or urgent surgery, it will not in all cases be possible to give the patient 24 hours to consider participation. However, all patients will be given enough time to read the written information, listen to the oral information and ask any questions. A similar setup is required in a randomized clinical trial, which we are currently conducting. The study includes patients in the acute phase of an acute myocardial infarction and was approved by “Den Videnskabetiske Komité, Region Hovedstaden” (Journal nummer: H-3-2010-117, EudraCT nummer: 2010-022400-53).

In the written information the amendment “Dine rettigheder som forsøgsperson i et biomedicinsk forskningsprojekt” from “Den Centrale Videnskabetiske Komité’s” pre-printed folder will be included. The patient will be encouraged to read this before giving his informed consent. It is central and important to investigate the remote ischemic preconditioning intervention in a group of acute patients. Patients that require acute surgery have a much higher risk than others for developing major cardiovascular complication. Therefore, it is of particular importance to investigate if this non-invasive intervention can improve the treatment and outcome for this group of high-risk patients.

### *Safety*

The use of a blood pressure cuff/tourniquet in remote ischemic preconditioning is considered completely safe. There is a small possibility of having skin erythema in the area where the inflated cuff was placed. In case of regional anesthesia, the patient can experience numbness and discomfort during the preconditioning procedure. The discomfort will be similar to a 5-minute blood pressure assessment. An identical preconditioning protocol was used in prior Danish clinical trials including patients with stroke [18] and acute myocardial infarction [19]. In one of the studies a questionnaire was designed to detect any discomfort created by the preconditioning [18]. No reports of significant discomfort were reported [18]. The numbness and skin erythema are both fully reversible and will rapidly wear off. There is a very small possibility of getting a skin infection or haematoma after having the blood samples taken. We will therefore use a standardised aseptic technique in trying to avoid this complication.

### *Ethical considerations*

We seek the approval from “den Videnskabetiske Komité” and “Datatilsynet”.

The ischemic intervention is considered completely safe, and has been done in previous large clinical trials [9, 10]. No serious adverse events have been reported [9, 10]. The patients will gain a personal benefit by participating if this simple and low-risk intervention is effective. The risk of myocardial injury and postoperative cardiovascular morbidity could be markedly reduced in the intervention group. The preconditioning procedure will not prolong the anesthetic time or delay the onset of surgery.

Participation in the trial is voluntary. Patients will be given oral and written information according to the Helsinki II declaration. The patients can, at any time, withdraw from the project, which will have no consequences for further treatment. The authorized healthcare professionals involved in the project will demonstrate diligence in their duties. The participating patients' integrity and autonomy will be respected. The trial will be carried out at the Department of Surgery, Zealand University Hospital.

*Duration:*

The trial is planned to initiate when all relevant approvals have been received (“Datatilsynet”, “den Videnskabetiske Komité”). We expect to include 4-6 subjects each week. We expect to start the trial in January 2014 and end it in January 2018.

*Economy:*

The patients will not receive any economic compensation for their participation.

The trial is initiated by: [name] (MD, PhD student), [name] (MD, professor, DMSc) from Department of Surgery, Zealand University Hospital and [name] (MD, Ph.D.) from Department of Anesthesiology, Zealand University Hospital.

*Funding*

The trial has received funding from:

|                                     |           |
|-------------------------------------|-----------|
| Toyota Fonden                       | 100.000kr |
| Beckett-Fonden                      | 100.000kr |
| Snedkermester Sophus Jacobsens Fond | 30.000kr  |

The study was designed and will be conducted, analyzed, interpreted, and reported independently of the funding sources.

*Budget*

| EXPENSES        | SPECIFICATION                                 | UNIT | PER UNIT/KR                    | TOTAL/KR   |
|------------------------|--|-------------|---------------------------------------|-------------------|
| EQUIPMENT       | Endopat 2000 (Itamar Medical Ltd., Caesarea, Israel) | 1           | 161,250                               | 161,250           |
|                        | Finger probes  | 2160        | 1,980kr/box with 12 units (180 boxes) | 356,400           |
| ANALYSIS        | Troponin I   | 2700        | 30                                    | 81,000            |
|                        | Pro-BNP  | 1080        | 180                                   | 194,400           |
| WAGES           | Scholarship  |             |                                       | 120,000           |
| SUM             |  |             |                                       | 913,050           |
| OVERHEAD (3.1%) |  |             |                                       | 28,304.55         |
| TOTAL           |  |             |                                       | 941,354.55 |

*Publication*

All results, positive as well as negative will be published in international journals with peer-review. Authors will all fulfill the ICMJE-guidelines for authorship.

Order of authors in all publications

1st author: [name]

2nd author: [name]

Last author: [name]

More authors may be added if they according to the authors listed fulfill the ICMJE-guidelines for authorship.

*The possible significance of the trial*

Perioperative myocardial infarction and myocardial injury in noncardiac surgery is more common than previously anticipated. At the moment no prevention or treatment is known and universally accepted. Remote ischemic preconditioning is a safe, cheap and a fast intervention, which can be easily implemented. If the intervention is effective, we can potentially reduce the perioperative and postoperative cardiovascular morbidity and mortality.

## Summary of Changes

### Protocol

| Amendment, date      | Details   |
|-----------------------------|--|
| 1. Amendment,
04.02.2015 | Adding the assessment of N-terminal pro-Brain Natriuretic Peptide (Zealand University Hospital trial site)   |
| 2. Amendment,
04.06.2015 | Adding a trial site (Regional Hospital West Jutland)
At the new trial site, high-sensitive troponin I was assessed.
Myocardial injury was defined as high-sensitive troponin I > 24 ng/L (99 th percentile URL, 14% CV) |
| 3. Amendment,
13.08.2015 | Adding a trial site (Herlev Hospital)
Excluding patients undergoing major abdominal surgery
Adding an assessment of endothelial function and coagulation markers   |
| 4. Amendment,
25.01.2016 | Adding the assessment of N-terminal pro-Brain Natriuretic Peptide (Regional Hospital West Jutland trial site)  |
| 5. Amendment,
29.12.2016 | Adding the exclusion criteria: "Other conditions that prevent the performance of remote ischemic preconditioning"
Expanding the clinical follow-up until 5 years after surgery  |

**Prevention of myocardial injury by remote ischemic preconditioning in emergent or urgent non-cardiac surgery: a randomized clinical trial**  
**The PIXIE study**

**Statistical analysis plan for the primary publication**

**Definitions of the population**

*Intention-to-treat:* randomized in the trial and a minimum of two postoperative troponin assessments within four days of surgery (an evaluable primary outcome)

*Per-protocol:* randomized in the trial, received the allocated treatment, and a minimum of two postoperative troponin assessments within four days of surgery

We will do a per-protocol analysis and an intention-to-treat analysis.

**The primary analysis**

Comparing the incidence of myocardial injury (No. (%)) in the intervention group versus the control group. We plan to use a chi-square test. The difference is considered to be significant if the two-sided p-value < 0.05.

**Secondary analyses**

All analyses compare the difference between the intervention group and the control group. Continuous outcomes will be analyzed with non-parametric (Wilcoxon two-sample test) or parametric statistics (unpaired t-test) depending on data distribution and equality of variances. If necessary data will be logarithm transformed. Continuous outcomes will be expressed as mean (95% confidence interval) or median (inter-quartile range). Categorical outcomes will be analyzed with a chi-square test or Fischer's exact test (an expected count < five in one cell) and the result will be expressed as no. (%). Differences are considered significant if the two-sided p-value < 0.05.

Secondary comparisons include

- Peak plasma troponin I within four days of surgery
- Total troponin I release (area under the curve) during the first four days after surgery
- Perioperative myocardial infarction

## **Original version**

- Major adverse cardiovascular events (30 days)
- Length of postoperative hospital stay
- Length of intensive care unit stay
- All-cause mortality (30 days)

## **Sample size**

We predict that 15% of the patients in the placebo group will suffer from myocardial injury and that the incidence of myocardial injury will be reduced to 7% in the intervention group. Type I error is set at 5% and type II error is set at 20%. In total 2 x 264 patients need to be included based on this power calculation. We will include patients until we have a total of 2 x 270 patients for evaluation (per-protocol).

We will do an interim analysis based on the primary outcome when a total of 270 (50%) evaluable patients have been included in the study. We will use the O'Brien Fleming method with a level of significance at  $p < 0.005$  (first analysis) and  $p < 0.048$  (second analysis).

**Prevention of myocardial injury by remote ischemic preconditioning in emergent or urgent non-cardiac surgery: a randomized clinical trial**  
**The PIXIE study**

**Statistical analysis plan for the primary publication**

**Definitions of the population**

*Intention-to-treat:* randomized in the trial and a minimum of two postoperative troponin assessments within four days of surgery (an evaluable primary outcome)

*Per-protocol:* randomized in the trial, received the allocated treatment, and a minimum of two postoperative troponin assessments within four days of surgery

We will do a per-protocol analysis and an intention-to-treat analysis.

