- Number of patients with peak plasma cardiac troponin I (cTnI)  $\geq$  45ng/L (99th percentile URL, 10% CV at 40ng/L) during surgery or during the first 4 days after surgery (perioperative myocardial injury). If elevated at baseline (preoperative) a 20% or greater increase of cTnI according to baseline is required for the diagnosis of a perioperative myocardial injury [15].
  - o Holstebro Hospital: Number of patients with peak plasma cardiac troponin I (cTnI) > 24 ng/L (99th percentile URL, 14% CV)

*Secondary outcome*

- Peak plasma cTnI and total cTnI release (area under the curve) during surgery or during the first 4 days after surgery
- Plasma N-terminal Pro-Brain Natriuretic Peptide (NT-proBNP) before surgery and at day 1 after surgery.
- Endothelial dysfunction assessed by the non-invasive EndoPat system (24 hours after surgery, only done at Zealand University Hospital)
- Biomarkers of coagulation (only patients included at Holstebro Hospital)
- Perioperative myocardial infarction (Universal definition of myocardial infarction, published in 2012 [15])
  - A typical rise or fall of cTnI with peak plasma cTnI  $\geq$  45ng/L (99th percentile URL, 10% CV at 40 ng/L) (Holstebro cTnI > 24 ng/L), and with at least one of the following:
    - Symptoms of ischemia

---

 Defined as a preoperative cTnI  $\geq$  45ng/L (99th percentile URL, 10% CV at 40ng/L)

- New or presumed new significant ST-segment-T wave (ST-T) changes or new left bundle branch block (LBBB)
  - Development of pathologic Q waves in the ECG
  - Imaging evidence of new loss of viable myocardium or new regional wall motion abnormality
  - Identification of an intracoronary thrombus by angiography or autopsy
- Cardiac death with symptoms suggestive of myocardial ischemia and presumed new ischemic ECG changes or new LBBB, but death occurred before cardiac biomarkers were obtained, or before cardiac biomarker values would be increased.
  - Development of new pathologic Q waves on an ECG or pathological findings of a healing myocardial infarction if troponin levels were obtained at times that could have missed the clinical event
- Major adverse cardiovascular events (30 days, one year and five years after surgery)

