### *Withdrawal criteria and dropouts*

The patient can at any time decide to discontinue his/hers participation in the trial. In case of major serious per- or postoperative complications/events, the investigator can decide to withdraw the patient from the trial for the sake of the patient.

The number of dropouts and withdrawals will be reported in the final manuscript and new participants will be included until 2 x 270 patients have completed the trial. In order to complete the protocol the patient must have received the intervention/placebo and have a minimum of two postoperative cTnI assessments done within the first 4 postoperative days (the primary outcome). If the primary outcome is missing the short- and long-term follow-up will still be done and the patient will be included in the final analysis (intention-to-treat analysis). The patient will dropout if reoperated within the first 4 postoperative days.

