## **Sample size**

We predict that 15% of the patients in the placebo group will suffer from myocardial injury and that the incidence of myocardial injury will be reduced to 7% in the intervention group. Type I error is set at 5% and type II error is set at 20%. In total 2 x 264 patients need to be included based on this power calculation. We will include patients until we have a total of 2 x 270 patients for evaluation (per-protocol).

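### The final SAP's intention-to-treat set requires two postoperative troponins, the protocol keeps patients with a missing primary outcome in that analysis, and the SAP defines no all-randomised set

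*Combined protocol and SAP*

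**What the plan says.** Final SAP, Definitions of the population. Two sets are defined. Intention-to-treat is "randomized in the trial and a minimum of two postoperative troponin assessments within four days of surgery (an evaluable primary outcome". Per-protocol has the same troponin condition and also requires that the allocated treatment was received. Both analyses are planned, and neither is named as the main one. The primary and secondary analysis sections name no population.

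Final SAP, Sample size: "We will include patients until we have a total of 2 x 270 patients for evaluation (per-protocol".

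Current protocol, Withdrawal criteria and dropouts:
- Completion: "In order to complete the protocol the patient must have received the intervention/placebo and have a minimum of two postoperative cTnI assessments", within four days. The same sentence labels this requirement as the primary outcome.
- Missing primary outcome: "the short- and long-term follow-up will still be done and the patient will be included in the final analysis (intention-to-treat analysis".
- Replacement: "new participants will be included until 2 x 270 patients have completed the trial".
- Reoperation: "The patient will dropout if reoperated within the first 4 postoperative days".
- After major serious complications, "the investigator can decide to withdraw the patient from the trial for the sake of the patient".

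Current protocol, Primary outcome. Injury is defined on the peak troponin, with a separate threshold at Holstebro. If baseline is elevated, "a 20% or greater increase of cTnI according to baseline is required for the diagnosis of a perioperative myocardial injury". Nothing in this definition needs two postoperative values.

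Current protocol, Participant timeline and Allocation and blinding. Troponin is drawn before surgery and on the mornings of days 1 to 4. Staff and patients are not blinded; assessors are.

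**The concern.** Having a second postoperative sample is something that happens after randomisation. Patients without one include those who die early, leave, or are withdrawn because of complications, and some of these reasons are close to the outcome. With unblinded staff and patients, balanced exclusions cannot be taken for granted. Assessor blinding and a laboratory assay protect the measurement; they do not determine who reaches a second sample.

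At stake is whether the analysis called intention-to-treat is one. Two analysts who followed the current documents faithfully could use different populations for the primary outcome, and different populations again for mortality, major adverse cardiovascular events (MACE) and myocardial infarction.

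**Working it through.** **1. Is the conflict in current text?** Yes. The troponin condition stands in both the original and the final SAP, and the rule for a missing primary outcome stands in both protocol versions. Neither summary of changes mentions the point, so this is not a clash between a superseded text and a current one.

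**2. Where does each kind of patient fall?** Reading the final SAP literally against the current protocol:

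| Patient | SAP intention-to-treat | SAP per-protocol | Protocol |
|---|---|---|---|
| Fewer than two postoperative troponins, outcome missing | out | out | followed, and in the intention-to-treat analysis |
| Dies or leaves before a second sample | out, hence possibly out of 30-day mortality, MACE and infarction | out | follow-up outcomes still to be recorded |
| One postoperative value that already meets the injury definition | out of the primary analysis | out | meets the outcome definition, but has not completed |
| Reoperated within four days, with two samples | in | in, if treated as allocated | dropout; analysis status not stated |
| Withdrawn by the investigator | depends on sample count | depends on sample count and treatment | analysis status not stated |

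**3. Which set is primary?** The SAP ranks neither. Its only hint is the per-protocol label on the 2 x 270 count. The protocol treats the same number as a recruitment target, and leans weakly the other way by attaching intention-to-treat to the final analysis.

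**4. The plan's own figure.** Inputs from the sample-size section: 15% versus 7%, two-sided 5%, 80% power. With mean risk 0.11,

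n = [1.960·√(2·0.11·0.89) + 0.842·√(0.15·0.85 + 0.07·0.93)]² / 0.08² = 239 after rounding up.

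The continuity correction, (n/4)·[1 + √(1 + 4/(0.08·n))]², gives 264 per arm, as stated. The sample size is not in question.

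**5. How much could selective exclusion matter?** The loss rates and the share of lost patients with injury are assumptions, because the documents give neither. Suppose there is no true effect, with 15% injury in both arms. If a fraction L of an arm is lost and a share f of the lost had injury, the risk seen in the analysed patients is

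(0.15 − L·f) / (1 − L).

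For L = 3% and f = 1 this is 0.12/0.97 = 12.37%. For L = 1% and f = 1 it is 0.14/0.99 = 14.14%. The chance of p < 0.05 was then found by exact binomial enumeration of the uncorrected chi-square test with 270 analysed per arm.

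| Losses in the two arms | f = 1 | f = 0.5 | f = 0.3 | f = 0.15 |
|---|---|---|---|---|
| none | 4.9% | – | – | – |
| 2% / 1% | 5.9% | 5.1% | 5.0% | 4.9% |
| 3% / 1% | 9.1% | 5.6% | 5.0% | 4.9% |
| 4% / 1% | 15.2% | 6.5% | 5.2% | 4.9% |
| 3% / 3% | 4.9% | 4.9% | 4.9% | 4.9% |

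In patients, 3% / 1% means about 8 lost against 3 (270/0.97 = 278; 270/0.99 = 273).

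**6. How fragile would one result be?** With invented counts, 40/270 control events against 24/270 gives p = 0.033. Restoring two excluded intervention patients, both injured, and none in control (26/272) gives p = 0.061. At about the planned rates, 40/270 against 19/270 (p = 0.004), seven such patients are needed (26/277, p = 0.051).

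**The case against.** The strongest case on the other side has four parts.

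**The protocol also ties the primary outcome to two samples.** Its rule on missing outcomes speaks first of follow-up, so it may mean only that such patients stay in for the follow-up outcomes. That reading is fair and narrows the conflict over the primary outcome. It does not remove the problem, because the SAP then has no set for those follow-up outcomes.

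**Few patients may be affected.** Troponin is scheduled on four mornings and two values suffice, so a patient must miss at least three. This stands. It does less for early death or withdrawal, where the remaining samples are lost together.

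**The effect is modest under milder assumptions.** With 30% of lost patients injured, twice the base risk, the error rate is 5.0% to 5.2%. The larger figures need every lost patient to be injured and losses to be three- or four-fold unequal. This also stands.

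**The SAP is not wholly silent on reoperation.** Read literally, it keeps a reoperated patient who has two samples. What is missing is the meaning of dropout for the analysis.

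A reader might go further and infer that the trial is biased, that per-protocol has been made the primary analysis, or that early deaths will certainly be left out of 30-day mortality. The documents support none of these. They give no loss rate by arm, the per-protocol label belongs to a recruitment count, and exclusion from mortality is only one reading of a SAP that names no population for it.

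**Conclusion.** The contradiction is real and should be fixed before analysis. The SAP's intention-to-treat set is an evaluable-outcome set. It conflicts with the protocol's rule on missing primary outcomes or, on the narrower reading, leaves the follow-up outcomes without a population. The SAP also ranks neither set.

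The size and direction of any bias cannot be derived. In the illustration, the false-positive rate moves from 4.9% to between 5.0% and 15.2% at losses of 3% / 1% or 4% / 1%, depending on how many of the lost had injury. It stays at 4.9% when losses are equal or when the lost carry the ordinary 15% risk. Material bias therefore needs losses that are both unequal between arms and concentrated in injured patients. The definitional conflict rests on the text alone; the magnitude rests wholly on the assumed loss patterns.

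**What to change.** Reconcile the protocol's withdrawal section with the SAP's population and sample-size sections:

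1. Define intention-to-treat as all randomised patients, analysed as allocated. Use it for 30-day mortality, 30-day MACE and myocardial infarction, and report missing follow-up by arm.
2. Rename the two-sample set evaluable (modified intention-to-treat).
3. State which set is primary for the troponin outcome. An as-allocated intention-to-treat analysis is preferable to per-protocol. Say that 2 x 270 is a recruitment target only.
4. In the all-randomised analysis of the primary outcome, count as an event any available postoperative value that meets the site's definition, including the 20% rise when baseline is elevated.
5. Keep patients with fewer than two samples and no positive value in the denominator by one named method. An example is multiple imputation by arm from baseline covariates and available troponins, with best-case and worst-case sensitivity analyses. Omitting them while counting single positive values would bias incidence upward, because only events would enter from that group.
6. State the analysis status of patients who drop out for reoperation or are withdrawn by the investigator, and whether follow-up continues after such a withdrawal.

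The cost is SAP wording and a little extra analysis. Follow-up of patients with a missing primary outcome is already planned. An all-randomised analysis of the primary outcome would rest partly on missing-data assumptions, and the evaluable-set analysis alongside it makes that dependence visible.
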